11.0 Specimen Collection and Banking

Videotapes will be stored for future use, by Drs. [name] and [name] in a password protected file on the pediatric server, behind MUSC's firewall. Future use will include education and teaching sessions and in presentations to describe the combined CIMT and taVNS treatment. They will be deidentified as much as possible although the therapist may use the infants name during CIMT. Only Drs. [name], [name] and [name] and study personnel will have access to subject identities. Only coded identifiers will be used to store and linked to videotapes. If parents wish to withdraw the infant videotapes at any age prior to 18 years, they may request to do so in writing, and withdraw any future use of the child's videotape. Videotapes will not be released to other parties not directly involved in research.

12.0 Data Management

Analysis and Statistical plan: We will compare the change in score on functional measures between CIMT+ taVNS via repeated measures ANOVA from pre- to immediately and 30 days post- treatment via ANOVA. Power analysis on primary outcome is not valid with 5-10 participants. However, for reference in infants treated with 60 vs 120h intensive CIMT⁸, the QUEST grasp mean changed from 4.50 ± 2.6 to 5.25 ± 3.1 with 3h/day CIMT ($\Delta=0.75$), versus 4.14 ± 2.6 to 5.73 ± 3.0 with 6h/day CIMT ($\Delta=1.59$). We estimate 40h of CIMT+taVNS, 2h/day CIMT+taVNS will be similar to 3h CIMT, Δ grasp = 0.75 .⁸

Keeping Data Confidential: We will assign study numbers to each participant, keep CRF and consent forms in locked offices. Database files with names and contact information will be password protected and stored on the MUSC Pediatric server. All other data files related to this study will be identified by participant number only, without link to standard identifiers. We will publish the aggregate data only.

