Limitations and alternative approaches: The therapist may provide feedback that a different trigger switch is needed or a different program with a '2min on-30sec-off' loop that does not require pressing the button repeatedly. We will then incorporate this feedback in our next design of the trigger. Previous NIH reviewers of our similar Soterix-based BabyStrong STTR phase I were concerned about overstimulation, requesting a fail-safe stop time for each trigger. We are using the same infant-modified Soterix taVNS unit, and for establishing safety in this CIMT+taVNS pilot we will use the same duty cycle of 2min-on, 30sec-off. For safety the taVNS unit limits deliverable microcurrent is limited to a maximum of 2mA, which is sufficient for adults to register a tingling. Feasibility of using wired ear electrodes: The infant should be engaged during CIMT such that the ear electrode does not irritate the infant. If the first infant does not tolerate the ear electrode, we will train infants on the electrode by having the mother place the electrode on the ear prior to the session and at home, to get the infant used to ignoring the presence of the electrode. The electrode should not impact hearing during the session. In our pilot trial infants received a hearing screen before discharge, all infants passed the screen except one, and that infant failed the hearing screen before taVNS treatment was initiated. No hearing adverse events were noted in that pilot trial.

Feasibility of delivering high fidelity CIMT with taVNS: We expect the therapist to maintain high fidelity of CIMT delivery while delivering taVNS over the weeks of treatment for the first infant. If the BSL RA has to assist in most therapy sessions after week 1, we will troubleshoot any sticking points and retrain the therapist so that the CIMT flow is minimally interrupted by triggering taVNS. If the therapist is not able to achieve high fidelity scores of 3 on all items by week 2 of treating the first infant, we will have the BSL RA assist with all sessions to ensure CIMT delivery, and if funds exist, incorporate design changes to increase therapist efficiency with the taVNS system during CIMT.

Aim 2: To measure infant response to low-dosage 40h CIMT + active taVNS stimulation (n=5) in: 1) upper extremity motor abilities, 2) gross motor skills, 3) individual treatment goals before and at the end of CIMT treatment. We will assess motor skills at 3mo after completion of CIMT for maintenance of gains.

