6.0 Number of Subjects

We will enroll up to 10 infants aiming to collect data on at least 5 completed courses of CIMT+taVNS.

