7.0 Setting

CIMT treatment sessions will occur in College of Health Professions (CHP) pediatric therapy lab located in the CHP B Building at [name].

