8.0 Recruitment Methods

We have IRB approval for two pilot studies (#67997, #103800) in preterm and term stroke/HIE infants with taVNS paired with feeding using similar taVNS study procedures as proposed in this application. The taVNS system has a non-significant risk device designation from MUSC's IRB in these two pilot trials.

[name] will screen for infants in the nursery with known brain injury that will likely lead to hemiparesis or weakness, such as perinatal arterial stroke, HIE, severe IVH, PVL or cerebellar infarct, regardless of sex or race. The clinical team will inform the parents of the potential to participate in the study. [name] will then explain the study to the parents and give them contact information if they are interested, to initiate screening and consent procedures when their infant reaches 6-8months of age. Infants are also referred directly to [name] and [name] specifically for CIMT from a wide region of the southeast. Because some parents travel great distances to get these services, we may obtain referrals from other care providers out of our region. We will perform phone screening and obtain Econsent prior to patient arrival for patients whose parents cannot meet in person prior to the first treatment session, to be able to get services fully prepared for the visit. We will use the approved REDcap system to obtain consent. [name] or other approved study personnel will go over the entire consent document on the phone with the parent to ensure comprehension and to confirm identity. Parent will be given a copy of the completed, signed consent form in person or by email or fax.

Volunteers of all ethnicities and racial categories will be accepted into this study protocol. No preference will be given based on race, gender or ethnicity. Young infants who had perinatal complications leading to perinatally acquired brain injury may be considered vulnerable populations and are the target of this proposal.

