The parents of infants who present for CIMT are highly motivated, and willing to commit to the time and effort commitment for CIMT. Most of the study procedures occur during the active treatment period. Therefore, we anticipate >95% retention to completion of the immediate outcome measures. For the 3 months follow-up assessment, we will call every month to discuss infant progress with the mother/caregiver. All of these infants will also have regular developmental follow-up in MUSC's or other high-risk clinic, and we will collect this data with parent consent, though it is not part of the primary or secondary outcomes for the phase I trial.

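### If the three-visit repeated-measures ANOVA is run in its classical form, an infant who misses the late visit is also lost from the pre-to-end comparison

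*Combined protocol and SAP*

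**What the plan says.** Section 12.0 (Data Management, analysis paragraph) compares functional measures "via repeated measures ANOVA from pre- to immediately and 30 days post- treatment via ANOVA". It names no mixed model, missing-data rule, analysis set or separate pre-to-end test. On sample size it says "Power analysis on primary outcome is not valid with 5-10 participants", and section 6.0 says "We will enroll up to 10 infants aiming to collect data on at least 5 completed courses of CIMT+taVNS".

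Aim 2, as set out in sections 1.0 and 3.0, has two parts. The first is response from before to the end of treatment. The second is persistence: "We will assess motor skills at 3mo after completion of CIMT for maintenance of gains".

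Section 8.0 covers retention. For the visit at the end of treatment, "we anticipate >95% retention to completion of the immediate outcome measures". For the later one, "For the 3 months follow-up assessment, we will call every month to discuss infant progress with the mother/caregiver", with no expected rate. The same section says of referrals: "Because some parents travel great distances to get these services, we may obtain referrals from other care providers out of our region". Section 7.0 places treatment on site: "CIMT treatment sessions will occur in College of Health Professions (CHP) pediatric therapy lab".

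The late assessment is at 30 days in section 12.0 and at 3 months in sections 1.0, 3.0, 8.0 and 10.0.

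**The concern.** The main efficacy question needs two scores per infant: before treatment and at its end. The named analysis adds a third visit. In the classical sum-of-squares form of repeated-measures ANOVA, an incomplete row is removed whole. An infant who finished the course and had both key assessments would then contribute nothing to the pre-to-end estimate, only because a later visit was missed.

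The late visit is plausibly the most exposed of the three. Treatment takes place on site over four consecutive weeks, so the first two assessments adjoin that stay, whereas the third requires a return. Some families are expected to come from far away, and the high retention figure stops at the end-of-treatment measures.

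The cost would be a wider interval around pre-to-end change, with no pre or end score actually missing. If families who return differ from those who do not, there could also be some selection. Section 1.0 says these pilot data are meant to precede a grant proposal, so the estimate and its interval are what the study will hand on.

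**Working it through.** **The plan's own figures.** Section 12.0 quotes reference changes in QUEST grasp. They reproduce: 5.25 − 4.50 = 0.75 and 5.73 − 4.14 = 1.59. The plan states no sample-size calculation, power or late-visit attrition to check.

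**Mechanism.** A classical repeated-measures ANOVA was run on 6 simulated subjects with 3 visits each; the error df were 10. With one late value deleted, the routine refused the data as unbalanced. It ran only after that subject was removed altogether, with error df of 8.

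**Inputs for size.**
- Number of infants: 5 (the completion target) and 10 (the enrolment ceiling), from section 6.0.
- Late visits missed: assumed 1 or 2 of 5, and 2 or 3 of 10.
- SD of the pre-to-end change: assumed unchanged by the loss, so results are in units of that SD.
- Two-sided 95% interval: assumed, as the plan states no level.

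**Formulas for the half-width of the pre-to-end interval.**
- Paired t, where the contrast has its own variance: t(0.975, n−1)/√n.
- Three-visit ANOVA with pooled error under sphericity: t(0.975, 2(n−1))/√n.

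| n | Paired t | Pooled ANOVA error |
|---|---|---|
| 5 | 2.776/√5 = 1.24 | 2.306/√5 = 1.03 |
| 4 | 3.182/√4 = 1.59 | 2.447/√4 = 1.22 |
| 3 | 4.303/√3 = 2.48 | 2.776/√3 = 1.60 |
| 10 | 2.262/√10 = 0.72 | 2.101/√10 = 0.66 |
| 8 | 2.365/√8 = 0.84 | 2.145/√8 = 0.76 |
| 7 | 2.447/√7 = 0.92 | 2.179/√7 = 0.82 |

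**Widening when late-visit misses remove infants** (from unrounded half-widths).

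| Infants kept | Paired t | Pooled ANOVA error |
|---|---|---|
| 5 to 4 | +28% | +19% |
| 5 to 3 | +100% | +55% |
| 10 to 8 | +17% | +14% |
| 10 to 7 | +29% | +24% |

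The pooled column is the one that matches the ANOVA named in the plan. The paired column applies only if pre-to-end change is tested with its own variance.

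**Chance of losing at least one infant.** With a missing rate m that is independent between infants, this is 1 − (1 − m)^N. The documents give no m, so a range is shown.

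| Assumed m | N = 5 | N = 10 |
|---|---|---|
| 5% | 23% | 40% |
| 10% | 41% | 65% |
| 20% | 67% | 89% |
| 30% | 83% | 97% |
| 40% | 92% | 99% |

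If exactly 5 infants complete treatment, the N = 5 column is also the chance that fewer than 5 remain in the analysis.

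**With the contrasts separated.** A missed late visit then removes nothing from pre-to-end. With 5 infants and one late visit missed, n stays at 5 and the paired half-width is 1.24 rather than 1.59 SDs of change.

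**The case against.** The strongest reply is that no section says incomplete infants will be deleted. The analysis text is one loose sentence and could be read as two changes, pre to immediate and pre to late. Aim 2 itself separates the two questions. That is fair, and it is why the point is conditional on the classical form. But the sentence names a repeated-measures ANOVA across the visits, and nothing else in the documents prevents the loss.

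Second, the retention text concerns a 3-month visit, while the analysis sentence uses 30 days. Read literally, a missed 3-month visit deletes nothing, because that score is not in the ANOVA. This stands as a separate conflict to be reconciled. It does not remove the point, since whichever late visit enters a classical ANOVA can cause the loss.

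Third, a reader might infer that the infants who remain would be mostly local. The documents do not support that. Section 8.0 says only that out-of-region referrals may occur and gives no share. No late-visit rate appears, and the same section describes motivated parents and plans monthly calls.

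A reader might also take the 28% to 100% widening as the effect of the planned ANOVA. Those figures belong to the paired t; pooled error gives 19% to 55%.

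Fourth, this is an open-label, single-arm pilot that disclaims a power analysis. That stands, and it sets the severity.

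**Conclusion.** The point holds conditionally. If the ANOVA is run classically and an infant misses the late visit, valid pre-to-end data are discarded and nothing in the plan prevents it.

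From 5 infants with 1 or 2 late visits missed, the pre-to-end interval widens by about 19% or 55% (pooled error, sphericity), or 28% or 100% (paired t). From 10 infants with 2 or 3 missed, it widens by about 14% or 24% (pooled), or 17% or 29% (paired). All of these assume an unchanged SD of change and an assumed number of missed visits.

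Some late-visit loss is plausible from the plan's own text. Its rate, and any selection by distance from the site, are assumptions. The harm is lost precision and possible selection, not lost power. Severity is low.

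**What to change.** In section 12.0, replace the single three-visit ANOVA with two stated contrasts: pre-to-end change on every infant with both of those scores, and the late-visit contrast on every infant with the scores it needs. Report n at each visit. A linear mixed model using all available scores, with visit as a category and small-sample degrees of freedom, is an acceptable alternative; the simple contrasts are easier to defend with 5 infants.

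In the same edit, reconcile the 30-day and 3-month timings so that it is clear which late visit is analysed.

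The cost is about one sentence of analysis wording and no new data. The small downside is that n may differ between the two contrasts, which the reported counts make visible.

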13.0 Provisions to Monitor the Data to Ensure the Safety of Subjects

Data and Safety Monitoring Plan

The participants who receive active taVNS involved with this proposal will be infants whose participation is agreed to by their guardians in written consent, and their mothers. The principal investigator will be responsible for monitoring the safety of the proposed experiments. [name] will also execute the Data Safety Management (DSM) plan and provide any necessary progress reports to the IRB, including but not limited to subject demographics, recruitment rates, retention rates, quality assurance issues, and adverse events or significant adverse events. [name] or her designee, should she be unavailable, will be responsible for reporting all unanticipated problems or AEs to the IRB. The PI or Co-I will be present for patient visits and the OT Research Assistant will discuss any perceived AE with them. [name] will be responsible for reporting any unanticipated device- related AE's to FDA. All screening data will be kept in a binder in [name] locked office. Screening data collected from participants who do not qualify for the study will be securely destroyed.

[name], who is a board-certified neurologist and psychiatrist, and [name] will oversee the use of the taVNS system. [name] will be immediately available to the RA to monitor safety and adverse events.

An independent Safety Monitoring Committee (SMC) will be formed to advise the study investigators. The SMC will review and evaluate accumulated study data to ensure safety, as in the pilot trial. They also will make recommendations concerning continuation, modification, or termination of any of the taVNS studies. It will be composed of [name] PT PhD and NM4R PI, [name], OT PhD; and [name], MUSC associate professor psychiatry and assistant provost with extensive VNS, TMS, and tDCS experience. The SMC and IRB will be notified immediately of any and all SAE's.

Drs. [name], [name] and [name] will obtain informed consent for mother and infant to participate, during which participants' guardians are fully advised on the research procedures to be used, the amount of time required of them, the possible risks and benefits of the procedures, their right to refuse their infant's participation in the study without prejudice, their right to terminate participation of their infant at any moment without prejudice, and the name and telephone number of the principal investigator. We will perform phone screening and obtain eConsent prior to patient arrival for patients whose parents cannot meet in person prior to the first treatment session, to be able to get services fully prepared for the visit. We will use the approved REDcap system to obtain consent. [name] or other approved study

personnel will go over the entire consent document on the phone with the parent to ensure comprehension and to confirm identity. Parent will be given a copy of the completed, signed consent form in person or by email or fax.

Regarding confidentiality, subjects' guardians are informed that the information they provide, as well as participation in the study, will be kept strictly confidential, with access limited to the research staff. We will check the infant's medical records to gather the following information: gestational age at birth, ventilator support, head ultrasound and MRI results, bottle feeding, infection, neonatal condition during labor and delivery, infant's treatments and conditions, and developmental progress.

The identity of subjects in databases will be protected with alphanumeric codes. All data will be kept in locked office or on secure servers designed for use and access by Brain Stimulation and Neonatology Lab members only. Database files with names and contact information will be password protected and stored on the MUSC Pediatric server. All other data files related to this study will be identified by participant number only, without link to standard identifiers.

Videotapes will be stored for future use, by [name] and [name] in a password protected file on the pediatric server, behind MUSC's firewall. Future use will include education and teaching sessions and in presentations to describe the combined CIMT and taVNS treatment. They will be deidentified as much as possible although the therapist may use the infants name during CIMT. Only Drs. [name], [name] and [name] and study personnel will have access to subject identities. Only coded identifiers will be used to store and linked to videotapes. If parents wish to withdraw the infant videotapes at any age prior to 18 years, they may request to do so in writing, and withdraw any future use of the child's videotape. Videotapes will not be released to other parties not directly involved in our research.

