Aim 1. To determine the feasibility and safety of taVNS in 6-18mo infants with unilateral motor weakness undergoing CIMT therapy in an open label pilot trial. The CIMT therapy sessions will be videotaped and a random weekly session (20% sessions) will be scored for CIMT treatment fidelity while the therapist is delivering taVNS. [name] will score these using a CIMT fidelity scoring system previously used in other studies.¹³ Scores that meet or exceed therapist goals indicate that taVNS can be delivered by the therapist while delivering high quality CIMT.

Aim 1 Procedures:

- 1) We will follow the following protocol for CIMT paired with taVNS with one OT therapist delivering CIMT with a brain stimulation research assistant (BSL-RA) supervising the delivery of taVNS:
- 2) Hydrogel electrodes are placed in front of tragus, and inner tragus/cymba chonchae, securing the wires behind head with tape, and placing wire under shirt.
- 3) CIMT and BSL therapists will establish perceptual threshold (PT) daily, increasing +0.1mA, until infant shows signs of tingling sensation.
- 4) We will treat with stimulation at 0.1mA<PT, 500μsec, 25Hz, during each CIMT session.
- 5) The OT therapist delivering CIMT will start stimulation by pushing the button for a continuous 2min-on, 30sec-off program (similar to taVNS-feeding settings^{16,17}), while administering CIMT. Trigger button is off for rest.
- 6) Impedance is constantly displayed on the Soterix unit (*good, moderate or poor*). If contact is *poor*, a beep alerts the therapist and the BSL RA will adjust the electrode to ensure contact and delivery of stimulation.
- 7) Both parent and OT will be queried by weekly questionnaire to assess their perception of ease of use, infant tolerance, general acceptance and any recommendations for improvement of taVNS delivery during the 4 weeks of CIMT therapy.

Table 1. Key Features of Routine Infant CIMT Program

Dosage	Each session will be 2 hours, 5 sessions each week, over 4 consecutive weeks for a total dosage of 40 hours.
Therapy setting	MUSC's pediatric OT lab, fully equipped with mats, benches, toys for pediatric rehabilitation equipment
Type of constraint	We fabricate custom-made hand splint/orthotics for the infant's less-affected hand and place a soft mitt on this splint, as we have used in prior CIMT trials. The constraint mitt will only be worn during the therapy sessions. ³⁶⁻³⁹

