Therapist	Highly trained therapists trained in the principles of pediatric CIMT ³⁸ will use immediate and varied reinforcement, primarily verbal praise, smiles, and supportive gestures, to sustain the infant's attention, engagement, and enjoyment, then "shape" a movement by using prompts and increasing the demands for greater precision, strength, fluency (coordination), and speed, using technique of "successive approximations". The therapist implements a "MR3 cycle," of Movement, Reinforcement, Repetition, and Refinement, used in the I-ACQUIRE Phase II clinical trial to progress the child in increments as skills increase
Components of infant CIMT	Sessions will actively engage the infant to initiate, attempt, repeat, practice, and refine a wide range of age developmentally appropriate skills and movements using the more-impaired arm and hand. Emphasis will be on engagement of the infant and the affected upper extremity in age- appropriate activities in positions of supine,

sessions	prone, sitting, quadruped, and supported standing.
Documentation for each session	Therapist will keep formal daily therapy logs and ask mothers to report on activities and progress at each session. Therapist and mothers will jointly review targeted therapy goals at each session.
Discharge program	Therapist and parents develop a practical written plan to maintain gains made during the CIMT program. The plan will involve motor skills and functional activities appropriate for the infant's age at discharge from the program.

Technical administration of taVNS: The therapist will need assistance with learning the taVNS trigger system and integrating it with CIMT. 1) We will provide training sessions for the single designated CIMT therapist who will perform all interventions before enrolling patients, and 2) the BSL RA will supervise and assist with taVNS treatments with each patient session. The brain stimulation RA will be trained to deliver stimulation, place the ear electrode for good impedance readings, and demonstrate this with [name] or [name] prior to supervising the CIMT therapist. We have several RAs who are experienced in infant taVNS who may also supervise any new RAs in the procedures. As part of this training, we have an instructional video for setting up the taVNS system with an infant.

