10.0 Study Design / Methods

Overall Study Design: This study will determine the feasibility, and safety of therapist-directed taVNS paired with CIMT therapy in n=10, 6-18month old infants with hemiplegia after perinatally acquired brain injury. We will measure the effect of active taVNS paired with 40 hours of CIMT on infant motor skills before and after treatment over a month, and follow up the motor skills over 3 months. All infants will receive active taVNS treatment. CIMT treatment is a non-research procedure, and motor and developmental testing are non-research procedures. taVNS is a research procedure. CIMT sessions will be videotaped, to measure the fidelity of CIMT delivery while the therapist is delivering taVNS to determine feasibility.

The alternative treatment is the usual and customary occupational therapy services. If parents wish, they may pursue CIMT therapy with local therapists, but there are very few qualified therapists in the area.

We will monitor for and mitigate following risks are present with this study: Risk of skin irritation, risk of discomfort, risk of slightly decreased heart rate, and risk of loss of confidentiality.

Risk of skin irritation: we will monitor the skin on the inner aspect of the left ear before and after each session, and will switch to the right ear if redness is present, and decrease the stimulation if redness persists.

Risk of discomfort: We will protect against the risk of discomfort by close monitoring. We will use the mother's perception of infant discomfort and infant signs of discomfort to determine the perceptual threshold, and then treat at 0.1mA less than this level of perception. If any infant seems to be in discomfort during the CIMT taVNS session, we will decrease the microcurrent by 0.1mA, as in our feeding taVNS trial in infants. We will use facial expression change, fidgety movements and infant vocalization as signs of behavioral discomfort, to indicate need for decreasing the microcurrent during the taVNS session.

We will not continuously monitor heart rate during the taVNS session, as our extensive HR data in infants show no bradycardia and no decrease in HR beyond 60 seconds after starting stimulation.

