Given the minimal risk of taVNS FDA approved/cleared devices, we anticipate that taVNS paired with CIMT will be a very safe procedure in infants. The potential risks will be clearly outlined in the informed consent document, as in our prior infant taVNS study. MUSC's IRB has previously determined our taVNS system to be minimal risk device. Nevertheless, there may be unknown risks with experimental procedures.

Risk of loss of confidentiality: We will assign study numbers to each participant, keep CRF and consent forms in locked offices. Database files with names and contact information will be password protected and stored on the MUSC Pediatric server. All other data files related to this study will be identified by participant number only, without link to standard identifiers. We will publish the aggregate data only.

This study will involve research on vulnerable subjects: mothers and their infants with perinatal brain injury, potentially as a result of maternal conditions during pregnancy.

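### Beyond ear skin, in-session discomfort and a weekly tolerance query, adverse events are not solicited and have no collection window, so a wider safety statement would be weakly supported

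*Combined protocol and SAP*

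**What the plan says.** Section 13.0 describes how adverse events come to the investigators: the PI or a Co-I attends visits, and "the OT Research Assistant will discuss any perceived AE with them". It then covers reporting of known events to the IRB, the FDA and the Safety Monitoring Committee (SMC). It gives no question, checklist, grading, attribution rule or start and end of collection.

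Three parent contacts are planned:

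- Each session (Section 3.0, Table 1): "Therapist will keep formal daily therapy logs and ask mothers to report on activities and progress at each session".
- Each week (Section 3.0, Aim 1 Procedures, step 7): "Both parent and OT will be queried by weekly questionnaire to assess their perception of ease of use, infant tolerance, general acceptance", together with suggestions for better taVNS delivery.
- In follow-up (Section 8.0): "we will call every month to discuss infant progress with the mother/caregiver".

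Some risks are actively checked. Section 10.0 states that "we will monitor the skin on the inner aspect of the left ear before and after each session". It names behavioural signs of discomfort to watch for and uses the mother's perception in setting the perceptual threshold. The safety and feasibility outcome in Section 4.0 is electrode tolerance and contact, with sustained discomfort that needs a lower current in fewer than 5% of sessions.

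Section 15.0 adds that "there may be unknown risks with experimental procedures".

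**The concern.** Aim 1 asks whether taVNS is safe in infants aged 6 to 18 months, who cannot describe symptoms. That question is wider than the in-session criterion in Section 4.0. The active checks target effects already anticipated: skin and discomfort. An unanticipated or delayed event at home would reach the record only if a parent mentioned it, if the weekly tolerance item happened to draw it out, or if staff noticed it later.

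At stake is any broad sentence in the Aim 1 report, in the material the SMC reviews, or in the planned NIH proposal, to the effect that taVNS was safe or had no adverse events. Events that were never asked about cannot be recovered at analysis.

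**Working it through.** **1. Staff-observed time.** Inputs from Table 1: 2 h per session, 5 sessions a week, 4 weeks. This gives 2 × 5 × 4 = 40 h, which matches the stated dosage, and 5 × 4 = 20 sessions per infant. A 28-day course has 28 × 24 = 672 h. Observed share: 40/672 = 6.0%. Unobserved: 632/672 = 94.0%. In the 3 months afterwards, the only regular study contact described before the 3-month assessment is the monthly call.

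**2. What the Section 4.0 criterion rests on.** With 5 to 10 infants (Section 6.0) there are 5 × 20 = 100 to 10 × 20 = 200 sessions. Fewer than 5% means fewer than 5 or fewer than 10 sessions. All of these fall inside observed time, so missed home events cannot change this result.

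**3. Coverage as described.**

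| Source | Stated content | Events since last contact? |
|---|---|---|
| Skin check, each session | Ear skin | Only redness still present |
| Discomfort monitoring | Named signs during session | No |
| Session report | Activities and progress | Not stated |
| Weekly questionnaire | Ease of use, tolerance, acceptance, suggestions | Not stated; item wording not given |
| Monthly call | Progress | Not stated |
| Section 13.0 | Events perceived and discussed at visits | Not solicited |

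**4. How incomplete capture acts (illustration only).** Let p be an infant's true risk of at least one between-session event and c the chance that it is recorded. Neither is in the documents. With independent infants, P(no infant has a recorded event) = (1 − pc)^n.

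| n | p | c = 1.00 | c = 0.50 | c = 0.25 |
|---|---|---|---|---|
| 5 | 0.20 | 0.33 | 0.59 | 0.77 |
| 5 | 0.40 | 0.08 | 0.33 | 0.59 |
| 10 | 0.20 | 0.11 | 0.35 | 0.60 |
| 10 | 0.40 | 0.01 | 0.11 | 0.35 |

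For example, n = 5, p = 0.20, c = 0.50 gives (1 − 0.10)^5 = 0.59. Lower capture always makes an empty record more likely. How much more depends wholly on the assumed p and c.

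**5. Limit set by sample size.** With complete capture and no events, the one-sided 95% upper bound is 1 − 0.05^(1/n): 45% for 0/5 and 26% for 0/10. Asking removes one weakness of a clean record but not this one.

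**6. A precedent in the document.** The feeding trial's safety outcomes were bradycardia, skin irritation and a pain-scale change. Its results report persistent discomfort in 3 of 228 sessions (1.3%), resolved by lowering current. Sections 2.0 and 15.0 nevertheless summarise that experience as free of adverse effects. Narrow measures can therefore turn into a broad statement.

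**The case against.** The strongest reply is that safety surveillance here is not passive. Skin checks are scheduled around every session, and a pre-session check can find redness that persisted or appeared at home. Discomfort is watched for with named signs. Parents are asked weekly about tolerance and see staff five times a week. Medical records are reviewed for treatments and conditions. The questionnaire and case report form are not reproduced, so silence about a question is not proof that it is absent.

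Much of this stands, and it rules out two stronger readings. A reader might infer that adverse events are captured only when staff perceive them at visits. The skin checks, discomfort monitoring and weekly tolerance query contradict that. A reader might also infer that a favourable Aim 1 result would mainly reflect not asking. The Section 4.0 criterion is directly observed in session, so that does not follow.

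What does not stand is the step from these checks to general event collection. They cover anticipated local effects and tolerance of delivery. Whether the tolerance item reaches time at home cannot be determined. The record review has no stated timing or adverse-event purpose. The frequent session contact is described as a report on activities and progress.

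It is also fair to object that wider questioning will pick up common background events, and that a study with no comparator cannot separate them from effects of taVNS. That argues for reporting them descriptively, outside the Section 4.0 criterion. It is not a reason to leave them unrecorded.

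**Conclusion.** The point holds in a limited form. As described, event collection outside ear skin, in-session discomfort and the weekly tolerance query is unsolicited and has no window. The Section 4.0 criterion is sound in this respect. A wider claim of safety, or of no adverse events between sessions or in follow-up, would be weakly supported and would lean towards a clean record.

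The gap covers about 94% of the hours in the treatment month, plus the 3-month follow-up. That figure measures unobserved time; it does not mean that 94% of events would be missed. The size of the lean is unknown, since the probabilities in the illustration use assumed event and capture rates.

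The conclusion assumes that the unreproduced questionnaire and forms contain no more than the protocol describes. If they already ask about events since the last contact, the remedy shrinks to stating that and adding the window. This is a worthwhile, inexpensive improvement to the plan.

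**What to change.** Amend Section 13.0, the session-documentation row of Table 1 and the follow-up text in Section 8.0 as follows:

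- At each session and each monthly call, ask one short fixed question: has the infant had any health event or medical visit since the last contact?
- State the collection window: from the first taVNS session through the 3-month assessment.
- Record onset, severity and investigator-judged relation to taVNS in the existing therapy log.
- Report these events descriptively beside the Section 4.0 criterion, not as part of it, and include them in the SMC reports.
- Limit any statement that no adverse events occurred to what was asked and over which period.

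The cost is a few minutes per contact, a log page and a short amendment, with no new visits. More minor background events will be recorded, and 5 to 10 infants in a single arm cannot show whether taVNS caused them. The report should say so.
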